Full Study Protocol

GENERAL INFORMATION

Using AI Risk Predictions to Nudge Flu Vaccination

[name].

[contact]

June 28, 2021

IRB#: 2021-0483

BACKGROUND AND OBJECTIVES

On average, 8% of the US population gets sick from flu each flu season (Tokars et al. 2018). Since 2010, the annual disease burden of influenza has included 9-45 million illnesses, 140,000-810,000 hospitalizations, and 12,000-61,000 deaths (CDC 2020). The CDC recommends the flu vaccination to everyone aged 6+ months, with rare exception; almost anyone can benefit from the vaccine, which can reduce illnesses, missed work, hospitalizations, and death (CDC 2019). Flu vaccination will be especially important for high-risk patients during the COVID-19 pandemic so that flu cases are reduced and resources conserved.

While most recover from influenza without treatment, the elderly, those with comorbidities, and other high-risk individuals can experience complications such as pneumonia, other respiratory illness, and death. Geisinger has partnered with Medial EarlySign (Medial; www.earlysing.com) to develop a machine learning (ML) algorithm to identify patients at risk for serious (moderate to severe) flu-associated complications on the basis of their existing electronic health record (EHR) data. The development of this algorithm was already approved through a separate Geisinger IRB application (**IRB number 2020-0211**). Additionally, Geisinger deployed this system in a field study during the 2020–21 flu season (**IRB number 2020-0290**) and contacted the identified patients with special messages (in addition to standard interventions conducted by the health system every flu season) to encourage vaccination. Geisinger will again deploy this system during the 2021-22 flu season.

Medial's algorithm is an example of how interoperable health information exchange (HIE)—the ability for health information technology to share patient data—can improve the efficiency and effectiveness of healthcare. However, patients may not appreciate these benefits or the fact that healthcare has become substantially more integrated and collaborative. A systematic review of patient privacy concerns about HIE found that 15-74% of patients expressed privacy concerns, depending on the study, and concluded that patient perspectives remain poorly understood. A flu outreach message that explicitly references a review of patient medical records might backfire as patients react poorly to a sense they have lost control of their health records, even though in this

case the use is intended to benefit their care.

There is conflicting evidence on how people respond to advice or information that comes from an algorithm or machine. Dietvorst et al. (2015) documented a pattern of "algorithm aversion," in which people choose inferior human over superior algorithmic forecasts, especially after they observed the algorithm make an error. In contrast, Logg et al. (2018) described "algorithm appreciation," in which people followed advice more when they thought it came from algorithms than when they thought it came from human beings. Finally, Bigman and Gray (2019) found aversion to algorithms that make "moral decisions," including a (fictitious) medical decision of choosing whether or not to operate on a high-risk patient. In our field experiment from the 2020-21 flu season, we found evidence of neither aversion nor appreciation: High-risk patients obtained vaccination at similar rates whether they were told their risk was determined by a computer algorithm or simply a review of their medical records (Shermohammed et al., 2021). At the same time, informing these patients about their risk status caused an increase and acceleration in flu vaccination compared with a care-as-usual control group. This suggests that informing patients about their risk status can be effective, but it is not evident that the increased vaccination rate went beyond what would have occurred with a flu vaccination message devoid of risk information. Therefore, the present study includes an active control message that encourages flu vaccination without revealing risk. The prior work varied the general description of how risk was identified, but it did not identify specific, personalized factors contributing to risk for individual patients. Providing such information increases the transparency, quantity, and prominence of risk factors, and it can build trust in the messages and their source. But it may also backfire, if patients have difficulty perceiving sensible connections between the explanations and the risk determination (Miller, 2019; Stubbs et al., 2007; Mercado et al., 2016). Next season's high-risk messages will include personalized risk factors identified as having the greatest predictive utility for patients' risk scores generated by the Medial ML model. The extent to which such explanatory information contributes to algorithm appreciation or aversion remains an open question.

Our specific aims are:

1. Evaluate whether providing influenza risk information to high-risk patients has a larger effect on vaccination rates than simple reminders (with no risk information).
2. Evaluate whether providing an explanation of the personalized factors that contributed to risk assessment specifically boosts vaccination.
3. Evaluate whether providing an explanation of the personalized factors that contributed to risk assessment results in aversion (as revealed in decreased vaccination) or appreciation (increased vaccination) of algorithm-based assessment, relative to a simple review of medical records.

PROCEDURES

Research Design

Patients from the high-risk sample (primary target population) will be randomly assigned to one of 5 study arms. Outcomes during the 2021-2022 flu season will be compared between study arms.

Study Population

There are 3 separate populations to consider in the current study: the primary target population that will be randomized into an experimental condition and potentially contacted, and two secondary populations who will not experience an intervention and will only be included for data analysis purposes.

1) Primary target population

Inclusion Criteria:

- Aged 18 or older
- Have been determined as high-risk through Medial's ML algorithm

Exclusion Criteria:

- Has contraindications for flu vaccination
- Note: we will respect opt-out communication preferences, but will include patients in the study if they haven't opted out of at least one communication modality employed

2) Secondary population A (data analysis only): Household members

Inclusion Criteria:

- Household members of primary target population
- Have data in Geisinger's electronic health records

3) Secondary population B (data analysis only): Sub-threshold risk

Inclusion Criteria:

- Same as primary target population, except that these patients' algorithmic risk scores fall just below the high-risk cutoff

Exclusion Criteria:

- Same as primary target population

Recruitment and Enrollment. All patients will be recruited and enrolled from Geisinger; MIT/NBER collaborators will not be involved in recruitment or enrollment. Patients meeting the primary target population criteria will be enrolled into one of the 5 experimental conditions. Anticipated enrollment number for this primary target population is 47,000. Only patients from this primary target population will be contacted. However, health record data will be accessed to assess secondary outcomes for household members of this target population (expected N of 234,000) and for patients whose risk scores were calculated by Medial's ML algorithm and determined to fall just below the high-risk cutoff (expected N of 47,000). This brings the total planned enrollment to 346,000 participants.

Detailed Study Procedures.

Eligible patients will be randomly assigned to one of 5 experimental conditions:

1. **No-Contact Control:** In this condition, patients will receive no additional pro-vaccination intervention beyond Geisinger's normal efforts. Note that these efforts include a variety of Marketing and other system campaigns designed to encourage all patients and members to get their flu shot. In addition, the Care Gaps team has an annual campaign to encourage flu shots that targets patients who are determined by a non-ML assessment that they are at high risk for complications and we expect there to be overlap between this group of patients and the ML high-risk group we will be contacting. (Because the Care Gaps team's high-risk patients are not told that they are at high risk or that they have been targeted, we are not concerned that this ongoing campaign will interfere with our ability to measure the effects of high-risk communication.)
2. **Reminder Control:** In this condition, patients will receive messages reminding them to get the flu shot without being advised of their risk status.
3. **High Risk Only:** In this condition, patients will receive messages telling them they are at high risk for flu complications without specifying how/why Geisinger believes this to be the case.
4. **High Risk Based on Medical Records:** In this condition, patients will receive messages telling them they have been identified to be at high risk for flu complications via analysis or review of their medical records, and they will be given one or more contributing risk factors from their medical record. This is an accurate statement, since it does not specify that a human conducted this review or analysis. However, we anticipate that most readers will assume it was a human rather than an algorithm, allowing us to compare attitudes towards human versus machine risk determination.
5. **High Risk Based on Algorithm:** In this condition, patients will receive messages telling them they have been identified to be at high risk for flu complications via analysis of their medical records by AI/ML, and they will be given one or more contributing risk factors from their medical record.

Risk factors included in messages for Arms 4 and 5 may vary in their level of specificity. Some factors may be *specific*, in that they mention a particular medical function or process (e.g. "medical condition(s) or procedure(s) related to breathing"). Other factors may be *general*, without mentioning the medical function or process (e.g. "medical condition(s) or procedure(s)"). We may test whether outcomes vary as a function of factor specificity. We

included examples of specific and general messages in this protocol, along with a dictionary of all factors that may be included in messages.

In the 2020–21 study, messages were signed “Your Geisinger Health Team.” In the present 2021–22 study, messages may be signed by the individual’s PCP of record or by a clinical leader.

The copy for risk messages is nearly identical to messages sent during the 2020-2021 flu season (**IRB number 2020-0290**) with 2 main differences: 1) explanatory factors are added to messages for patients in Arms 4 and 5, and 2) the messages are written as if from a PCP rather than a team (e.g., “We are writing...” was changed to “I am writing...”).

Because this intervention is timed to the 2021–22 flu season, the intervention period will begin ~9/1/21. Subjects in treatment Arms #2–5 will receive the same type of communication via up to three modalities—printed letters to their mailing addresses, SMS to their mobile phones, and/or secure messages via Geisinger’s patient portal—depending on what consent and information is on file for each patient. Messages will be staggered by modality, starting with postal letters, then sending the same message via the patient portal two weeks later, and a final message via SMS after four weeks.

The primary outcome will be whether the patient was vaccinated during the first six weeks after the intervention begins. A secondary outcome will be vaccination within three months after the intervention begins. Additional secondary outcomes to be measured through the end of the flu season (start of intervention through 3/31/22) will include: rates of flu diagnoses (both using the most rigorous biological tests, “high confidence flu”, and using broader criteria that also include diagnosis codes and treatment information, “likely flu”), flu complications, and rates of other relevant healthcare utilization outcomes such as ER visits, hospitalizations, insurance claims (for an expected ~40% of participants who are members of Geisinger Health Plan) by patients, household members of patients, and those at sub-threshold risk. We will also measure rates of flu vaccination by fellow household members of targeted patients and non-targeted patients at sub-threshold risk. Finally, we will measure rates of COVID-19 vaccination in targeted patients, household members, and those at sub-threshold risk.

Data Sources

In order to identify patients in the primary target population, **Business Intelligence & Advanced Analytics** (BIAA), working with **Geisinger’s Phenomics and Clinical Data Core** (PACDC), will provide a list of patients (including patient identifiers such as Medical Record Number) that were assessed by the Medial and each patient’s associated risks.

We will also obtain contact information (address, phone number, email address) to message participants in the primary target population from BIAA & PACDC.

After the intervention is complete, we will obtain experimental outcome data for all 3 population groups from BIAA & PACDC. This will include data on patient flu vaccination, diagnosis of flu, diagnosis of flu-like symptoms, presence of flu-associated complications, hospital visits,

emergency department visits, and covid vaccination status. This data set will additionally include patient characteristics that will be useful as analysis covariates, such as: age, patient primary care provider, and flu-related behavior and outcomes during previous flu seasons.

STUDY DATA DETAILS

Data Management Procedures and Confidentiality. All data will be electronic. Datasets with full identifying information will only be stored on Geisinger-managed, password-protected computers of the data brokers ([name] and [name]) for the purpose of linking datasets from different sources.

A limited data set containing dates of service and ZIP codes will be shared with any non-Geisinger collaborators (e.g., Additional Principal Investigator [name] and his team) under a Data Use Agreement (pending approval) in compliance with HIPAA's Privacy Rule, and using data security protocols reviewed and approved by the Geisinger Security Office, Privacy Office, and Information Technology department.

After all data have been linked in a de-identified, coded file and analyzed, the datasets with identifiable information and any codes needed to link the identifiable information will be deleted. After the de-identified data have been fully analyzed, the de-identified dataset will be shared along with publications from this study. The deidentified data will not be destroyed or removed after any prespecified period of time has elapsed. We intend to permanently and securely archive the deidentified dataset at a research repository such as Open Science Framework (OSF) in order to be consistent with the best practices for open and reproducible science, as well as our obligation to the public as NIA-funded researchers.

The only study team members who will have access to fully identifiable and protected health information will be [name] and [name]. Non-Geisinger collaborators will have access to a limited data set containing dates of service and ZIP codes. The remaining investigators will have access to the de-identified, coded data during data analysis.

Using Explainable AI Risk Predictions to Nudge Influenza Vaccine Uptake

NCT05009251

11/10/2021

Protocol and Statistical Analysis Plan

Brief Summary

The study team previously demonstrated that patients are more likely to receive flu vaccine after learning that they are at high risk for flu complications. Building on this past work, the present study will explore whether providing reasons that patients are considered high risk for flu complications (a) further increases the likelihood they will receive flu vaccine and (b) decreases the likelihood that they receive diagnoses of flu and/or flu-like symptoms in the ensuing flu season. It will also examine whether informing patients that their high-risk status was determined by analyzing their medical records or by an artificial intelligence (AI) / machine-learning (ML) algorithm analyzing their medical records will affect the likelihood of receiving the flu vaccine or diagnoses of flu and/or flu-like symptoms.

Power analysis

The study team planned to enroll about 9400 patients per group, and a total of 47,000 patients across all 5 groups in the study. Assuming a baseline vaccination rate of 40% (based on baseline vaccination rate from our previous study), this sample would allow 80% power to detect 2% absolute difference, or a 5% relative difference, between two groups.

Sample and Randomization

The sample was slightly smaller than planned, with 45,164 patients total in the top 10% of risk for flu and flu-related complications among Geisinger patients who were over age 18.

The sample was first divided into those in the top 3% and those in the next lower 7% of risk (henceforth “top 10%”, the label used when subjects are contacted). Each of those groups (top 3%, top 10%) were randomized into one of 5 groups:

1. No-contact control - no messages were sent
2. Reminder control - message(s) encouraging the patient to get a flu shot but not mentioning anything about risk
3. High Risk Only - message(s) disclosing the patient's *high-risk status*, with no information about how their risk status was determined
4. High Risk with Explanation Based on Medical Records - message(s) disclosing the patient's *high-risk status* with the added explanation that they are at high risk based on a *review of their medical records* and with the top *reason(s) why they are considered high risk*
5. High Risk with Explanation Based on Algorithm - message(s) disclosing the patient's *high-risk status* with the added explanation that they are at high risk based on a *computer algorithm review of their medical records* and with the top *reason(s) why they are considered high risk*

Patients in groups 4 and 5 were further randomized to receive one reason or three reasons why they were at high risk (per the medical record review or the algorithm). Randomization occurred separately within each risk and message group. For example, in group 5 (algorithm) half of patients in the top 3% of risk received messages including one reason, while the other half received messages with three reasons.

Message modalities

Patients randomized to groups 2-5 were sent messages in up to 3 modalities: 1. a letter, 2. a myGeisinger (myChart patient portal) message, and 3. an SMS (text) message. Patients with a valid address on file were sent a letter. Patients were sent a myGeisinger message and/or an SMS if they were eligible and if their letter was not returned to sender.

Project status

All intervention messages have been sent. Data collection is ongoing. The study team has not yet extracted or analyzed any outcome data from the study.

Planned Analyses

Primary Outcome

Flu vaccination at 2 weeks after the final outreach date [Time Frame: Within 2 weeks of the final outreach date, 8 weeks + 1 day after the study start] *

Question 1: Does informing patients that they are at high risk for flu and flu-related complications increase the likelihood that they will get vaccinated?

Analysis 1a (Confirmatory): We will test the hypothesis that patients who were sent messages with information about their risk status (patients randomized to message group 3, 4, or 5) will exhibit improved flu vaccination rates compared with patients who were sent messages without risk information (group 2).

Analysis 1b (Confirmatory): We will test the hypothesis that patients who were sent messages with information about their risk status (those in group 3, 4, or 5) will exhibit improved flu vaccination rates compared with patients assigned to the no-contact control group (group 1).

For analyses 1a and 1b, we will run OLS regressions. For both regressions, we will include a binary predictor variable coding separately for baseline (group 2 for analysis 1a and group 1 for analysis 1b), and message (all patients in groups 3-5).

Question 2: Are flu shot messages more effective when they include reasons why (i.e., a medical records review or AI/ML-based review, along with personalized contributing risk factors) patients were designated as high risk for flu and flu-related complications?

Analysis 2 (Confirmatory): We will test the hypothesis that messages including reasons why patients are high risk (groups 4 and 5) are more effective at promoting flu shot uptake than messages that mention patients' risk status but do not include reasons (group 3).

To test this hypothesis, we will run an OLS regression with a categorical predictor variable (group 3 vs. group 4 or group 5).

Question 3: Do messages encouraging flu shots increase flu vaccination rates?

Analysis 3 (Confirmatory): We hypothesize that patients who were sent control messages encouraging them to get a flu shot with no information about their risk status (group 2) will be more likely to get a flu shot than those in the no-contact control group (group 1). To assess this hypothesis, we will employ OLS regression with a categorical predictor variable coding for group.

Question 4: Among messages that mention patients' risk statuses, is it most effective to a) give patients no information about how their risk status was determined (group 3), b) tell patients their high-risk designation was based on a review of their medical records with personalized reasons for their risk determination (group 4), or c) tell patients their high-risk designation was based on a computer algorithm review of their records with personalized reasons for their risk determination (group 5)?

Analysis 4 (Exploratory): We will evaluate this question using an OLS regression model, with a categorical predictor variable coding for group (group 3, group 4, group 5). We will run post-hoc tests using Tukey's HSD to test for significant pairwise differences between the groups.

Note that we designate Analysis 4 as exploratory, as similar messages in the 2020-21 flu season did not yield significant differences in flu shot uptake, and there is no clear guidance from the literature regarding specific expectations. Moreover, this year's messages are different from last year's in two ways that could yield different results: (1) This year's messages were signed by a named physician (either the participants' primary care providers or a clinical leader), whereas last year's messages were signed from "Your Geisinger Care Team"; and (2) In groups 4 and 5, messages included personalized reasons why patients were designated as high risk.

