We will also rerun the OLS regression analyses including a binary covariate for whether each patient has an assigned Primary Care Provider (PCP) who works at Geisinger, as flu shot data in the Geisinger EHR may be less reliable from those with an external PCP.

Finally, as an additional robustness check, we will run OLS regression analyses controlling for sex, 10-year age bins, and interactions among sex and age as covariates.

Secondary outcomes

We will use the approaches described in analyses 1-4 above to evaluate the impact of the intervention on the secondary outcome measures listed in the pre-registration:

1. Flu vaccination at 9 weeks after the final outreach date [Time Frame: Within 9 weeks of the final outreach date, within 15 weeks + 1 day of the study start] *

Received a flu vaccination

2. Flu diagnosis [Time Frame: 8 months (between September 9, 2021 and April 30, 2022)]

Received a "high confidence flu" diagnosis (with positive polymerase chain reaction [PCR]/antigen/molecular test) and/or "likely flu" diagnosis (as assessed via International Classification of Disease [ICD] codes or Tamiflu administration or positive PCR/antigen/molecular test)

3. Flu complications [Time Frame: 11 months (between September 9, 2021 and July 31, 2022)]

Diagnosed with flu-related complications

4. Healthcare utilization [Time Frame: 11 months (between September 9, 2021 and July 31, 2022)]

Visited ER, was hospitalized, or had flu-related insurance claims

*Because our outreach timeline was delayed (see above), we will delay the time frame for Secondary Outcome 1 from 3 months following the study start to 9 weeks following the final outreach date.

Additional exploratory analyses

1. Number of reasons

Patients in groups 4 and 5 were randomized to receive either 1 or 3 of the top reasons why they were considered high risk for flu. We will run an OLS regression testing for main effects and interactions between the number of reasons (1 reason, 3 reasons) and message type (group 4: medical records message, group 5: algorithm message) on flu vaccination.

2. Age

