Contraindicated patients: We unintentionally failed to remove a small number of patients contraindicated for flu vaccines from the sample prior to sending letters. After the error was discovered (after letters were sent, but prior to myGeisinger or SMS messages), because this was an exclusion criterion for the study, we removed the patients completely from the study, including from all analyses.

Patients deceased prior to our study start date (9/9/21): Midway through the study, we received an updated list of patients who were deceased. Some had died prior to the study beginning but medical records had not yet been updated to reflect the date of death. These patients will be removed from all analyses.

The following groups of patients will be excluded from all analyses, except the intent-to-treat analysis (robustness analysis) as described above:

Patients deceased during the study: A very small number of patients were recorded as deceased between the date we originally pulled the data and the date of the updated pull. These patients will be removed from analyses.

Patients sent protective risk reasons: Additionally, in determining the reasons each person was considered high risk, we unintentionally included reasons that were negatively weighted for a small number of patients. That is, for these patients, one or two of the reasons listed for their high-risk determination were *protective* against flu, despite their overall high-risk designation by the model. These patients will be removed because their messages may have been confusing and were not the precise messages we originally intended to send. For consistency across groups, we will also remove those in groups who were not sent reasons, but who would have received protective risk reasons had reasons been included in their messages.

Patients vaccinated prior to the study beginning: Area pharmacies and some Geisinger clinics began offering flu vaccines prior to our study beginning. We will remove patients from analysis who received a flu shot prior to 9/9/21, the study start date.

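### The primary models contain only study arm, leaving unused the prior-season flu history planned for extraction and the randomisation stratum; estimates stay unbiased but power is given up

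*SAP*

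**What the plan says.** Under Planned Analyses, each primary-outcome model has arm as its only predictor:

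- Analyses 1a and 1b: "we will include a binary predictor variable coding separately for baseline (group 2 for analysis 1a and group 1 for analysis 1b), and message".
- Analysis 2: "we will run an OLS regression with a categorical predictor variable (group 3 vs. group 4 or group 5".
- Analysis 3: "we will employ OLS regression with a categorical predictor variable coding for group".
- Analysis 4 (exploratory): a three-level arm factor with Tukey comparisons.

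Under Sample and Randomization, the sample is split into the top 3% and the next 7% of risk, and "Each of those groups (top 3%, top 10%) were randomized into one of 5 groups". The one-versus-three-reasons split in groups 4 and 5 was also made within risk group. No primary, robustness, secondary or exploratory model contains the stratum.

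The protocol (Data Sources) gives examples of patient characteristics it expects to be useful as covariates: "age, patient primary care provider, and flu-related behavior and outcomes during previous flu seasons". The SAP's adjusted reruns, under Sensitivity analyses and robustness checks, use a Geisinger-PCP flag and, separately, a model "controlling for sex, 10-year age bins, and interactions among sex and age as covariates". Age also appears as an exploratory moderator. Prior-season flu history appears in no model.

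**The concern.** Whether a patient was vaccinated last season is a natural candidate for the strongest available predictor of vaccination this season. Leaving it out does not bias a randomised comparison, but its share of the outcome variance stays in the standard error. Enrolment is closed and the sample fell short of plan, so covariate adjustment is one of the few remaining ways to gain precision.

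For a given R² the standard error shrinks by the same proportion in every analysis. The effect on power differs, because the comparisons start with different amounts to spare. Analysis 3 compares one arm with one arm and has the least margin of the confirmatory tests. The Tukey-adjusted pairs in Analysis 4 have less still, and they include records versus algorithm, which is the protocol's third aim.

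The stratum is a separate and smaller matter: an analysis should normally reflect how patients were randomised.

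**Working it through.** **Inputs.** From the SAP: 40% baseline, a 2-point target, about 9,400 planned per group, and 45,164 patients achieved. Assumed: an equal split (45,164/5 ≈ 9,033 per arm) and two-sided 5% tests, since the SAP gives neither realised arm sizes nor alpha.

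**The SAP's own figure.** With 9,400 per group and 40% versus 42%, power is 79.6%, so the stated 80% reproduces. A one-sided test would need only 7,477 per group, which does not match.

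**Formula.** SE = √[(0.40×0.60/n₁ + 0.42×0.58/n₂)(1 − R²)] and power = Φ(0.02/SE − c), where c = 1.96, or 2.344 for a Tukey pair among three arms.

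Example, Analysis 3 unadjusted: SE = √(0.4836/9,033) = 0.00732; 0.02/0.00732 − 1.96 = 0.77; power 78.0%.

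| Comparison | Unadjusted SE (points) | Power (%), R² = 0 | 0.05 | 0.09 | 0.25 | 0.40 |
|---|---|---|---|---|---|---|
| Analysis 3 (1:1) | 0.732 | 78.0 | 80.1 | 81.7 | 88.4 | 94.2 |
| Analysis 2 (1:2) | 0.633 | 88.5 | 90.0 | 91.2 | 95.4 | 98.3 |
| Analyses 1a/1b (1:3) | 0.596 | 91.8 | 93.1 | 94.0 | 97.2 | 99.1 |
| Analysis 4, one Tukey pair | 0.732 | 65.2 | 67.7 | 69.9 | 79.2 | 88.2 |

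**What the R² values mean.** The documents give none, so they are assumptions. For a binary covariate with prevalence π, R² = π(1−π)×gap²/0.24. At 40% prior vaccination this reduces to R² = gap², so 0.05, 0.09, 0.25 and 0.40 correspond to uptake gaps of about 22, 30, 50 and 63 points between patients with and without prior vaccination. An R² of 0.25 is worth 9,033/0.75 − 9,033 ≈ 3,000 extra patients per arm.

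**After exclusions.** The SAP does not give the number excluded. If 5% to 20% are lost (assumed), Analysis 3 starts at 76% to 69%. It reaches 80% to 73% at R² = 0.09, or 87% to 81% at R² = 0.25.

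**Stratum alone.** Take a 30/70 split, so R² = 0.21×gap²/0.24. Stratified randomisation has already reduced the true SE, so with s the nominal SE the unadjusted test has power Φ[(0.02 − 1.96s)/(s√(1−R²))] and Type I error 2Φ(−1.96/√(1−R²)). For assumed gaps of 5, 10, 15 and 20 points, including the stratum adds 0.06, 0.25, 0.57 and 1.02 points of power in Analysis 3. The unadjusted Type I error is 4.97%, 4.90%, 4.78% and 4.60%, which is slightly conservative.

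**Simulation.** 1,500 stratified 1:1 trials were run with 9,033 per arm, a true effect of 2.0 points, a 5-point stratum gap, 50% prior vaccination and a 50-point gap by prior vaccination (R² about 0.26).

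- Arm only: mean estimate 1.97, mean model SE 0.732, power 77.7%.
- Arm and stratum: power 77.7%.
- Arm, stratum and prior vaccination: mean estimate 1.98, mean model SE 0.629, power 87.7%.

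With a 30-point gap by prior vaccination and a 10-point stratum gap (1,000 trials), Analysis 3 power was 76.7%, 76.7% and 79.8% for the same three models. With that many trials the simulation error is about 1.3 points.

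**The case against.** The strongest reply is that nothing here is wrong. A prespecified arm-only difference in a randomised trial of 45,164 is unbiased and valid, and adjustment is a choice about efficiency. That stands, and it limits how serious the point can be.

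Several narrower objections also have force:

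- **The gain is assumed.** At R² = 0.05 Analysis 3 gains only about 2 points, and the 94% needs a gap of about 63 points. Removing patients already vaccinated ("We will remove patients from analysis who received a flu shot prior to 9/9/21, the study start date"), the short outcome window, and less reliable records for patients with an external PCP could each change the association.
- **The shortfall is small.** Before exclusions, the difference detectable with 80% power in Analysis 3 is 2.05 points. With 20% excluded and R² = 0.09, adjustment still leaves power at 73%.
- **The protocol is not contradicted.** Its covariates are examples, and two of the three, age and PCP, have counterparts in the robustness reruns.
- **The SAP sets no power target for Analysis 4.** The 65% applies the 2-point target to an exploratory comparison.

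None of these is a reason to leave the covariate out. At this sample size one or two baseline terms cost essentially no degrees of freedom, so the downside is negligible even if R² proves small. The existing reruns contain neither prior-season history nor the stratum. Logistic reruns with covariates would give conditional odds ratios, but in a robustness check that is a matter of labelling.

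**Conclusion.** The point holds as a loss of efficiency, with no bias and no inflation of Type I error. The primary specifications omit a covariate that the protocol plans to obtain and a stratum used in the randomisation.

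Before exclusions, Analysis 3 is the only confirmatory comparison below the SAP's 80% at its own 2-point target. Adjustment for prior vaccination would put it at 80% or above across the assumed R² range. Analyses 2, 1a and 1b have less to gain. The size rests on the assumed R², an equal split and two-sided 5% tests; the direction depends only on prior vaccination predicting current vaccination. The stratum matters for consistency with the design and contributes almost nothing to power. The change should be made, but the plan is not invalid without it.

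**What to change.** Before outcome extraction, amend the SAP as follows:

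- Make the primary specification of Analyses 1a, 1b, 2, 3 and 4, and of the number-of-reasons model, arm (with number of reasons and its interaction where relevant), a top-3% stratum indicator, and recorded 2020-21 season flu vaccination, with heteroskedasticity-robust standard errors.
- Code vaccination history as recorded versus none recorded. Add a missing-history category only if the EHR can distinguish it.
- Define the history so that 2021-22 season doses given before 9/9/21 do not count. Patients with such doses are excluded from the main analyses but return in the intent-to-treat check.
- Keep the arm-only models as a robustness check.
- Label any arm-by-stratum terms as exploratory effect modification by risk stratum. They cannot isolate the effect of the risk label, which was not randomised and coincides with actual risk.

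The cost is SAP wording. The stratum is already held, and prior-season behaviour is in the planned data pull. The SAP's Project status section records that "The study team has not yet extracted or analyzed any outcome data from the study", so on its own account the change could still be prespecified.
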